2.2. Objectives

Study objectives (Stage I):

1. Establish the frequency and severity of adverse events following the administration of single ascending doses of BCD-131 to healthy volunteers.
2. Establish key pharmacokinetic (PK) parameters ($AUC_{0-1176\text{ h}}$, $AUC_{0-\infty}$, C_{\max} , T_{\max} , $T_{1/2}$, K_{el} and CL) of BCD-131 following the administration of single ascending doses of the drug product to healthy volunteers.
3. Establish pharmacodynamic (PD) parameters ($AUEC_{0-1176\text{ h}}$, $AC-E_{\max}$) of BCD-131 based on the absolute reticulocyte count and Hb values in the blood of healthy volunteers following the administration of single ascending doses of BCD-131.
4. Study serum levels of binding antibodies (BAbs) in the blood of healthy volunteers following the subcutaneous administration of single ascending doses of BCD-131.
5. Establish main PK ($AUC_{0-1176\text{ h}}$, $AUC_{0-\infty}$, C_{\max} , T_{\max} , $T_{1/2}$, K_{el} and CL) and PD parameters ($AUEC_{0-1176\text{ h}}$, $AC-E_{\max}$ based on changes in the absolute reticulocyte count and Hb levels in the blood) as well as immunogenicity of therapeutic doses of Mircera® and Aranesp® given as subcutaneous injections to healthy volunteers.
6. Establish a safe dose of subcutaneous BCD-131 to be used at stage II of the study.

Study objectives (Stage II):

CONFIDENTIAL

Version 1.0 dated 21-Sep-2015

Page 4 of 21

1. Establish key pharmacokinetic parameters ($AUC_{0-1176\text{ h}}$, $AUC_{0-\infty}$, C_{\max} , T_{\max} , $T_{1/2}$, K_{el} and CL) of BCD-131 given as a single subcutaneous or intravenous injection to healthy volunteers at a dose established at stage I of the study.
2. Establish key pharmacodynamic parameters ($AUEC_{0-1176\text{ h}}$, $AC-E_{\max}$ based on changes in the absolute reticulocyte count and Hb levels in the blood) of BCD-131 given as a single subcutaneous or intravenous injection to healthy volunteers at a dose established at stage I of the study.
3. Establish the frequency and severity of adverse events and evaluate the level of BAbs to BCD-131 given as a single subcutaneous or intravenous injection to healthy volunteers at a dose established at stage I of the study.
4. Establish subcutaneous and intravenous doses of BCD-131 to be used in a phase II clinical study.

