3. STUDY DESIGN

3.1 Design

Stage I

Stage I of clinical study BCD-131-1 is an open-label, non-randomized clinical study of pharmacokinetics, pharmacodynamics, tolerability, safety and immunogenicity of the novel drug product given to healthy volunteers at ascending doses (Phase 1, a traditional “3+3” design). Also, at stage I the investigators will evaluate the PK and PD parameters of the closest analogues of BCD-131 (Mircera[®] and Aranesp[®]) given as subcutaneous injections at therapeutic doses.

Volunteers (no more than 54 subjects at stage I) will be included in the study after they have signed an informed consent form, completed an examination at screening (no more than 14 days) and received the approval of the investigator confirming their eligibility for the study.

Evaluation of pharmacokinetics, pharmacodynamics and safety of ascending doses of BCD-131

The evaluation of pharmacokinetics, safety and tolerability of BCD-131 will be conducted in 8 cohorts:

1. Cohort 01 will include no more than 6 volunteers who will receive a single subcutaneous injection of BCD-131 at a dose of 0.05 µg/kg body weight.
2. Cohort 02 will include no more than 6 volunteers who will receive a single subcutaneous injection of BCD-131 at a dose of 0.15 µg/kg body weight.
3. Cohort 03 will include no more than 6 volunteers who will receive a single subcutaneous injection of BCD-131 at a dose of 0.40 µg/kg body weight.
4. Cohort 04 will include no more than 6 volunteers who will receive a single subcutaneous injection of BCD-131 at a dose of 1.05 µg/kg body weight.
5. Cohort 05 will include no more than 6 volunteers who will receive a single subcutaneous injection of BCD-131 at a dose of 1.70 µg/kg body weight.
6. Cohort 06 will include no more than 6 volunteers who will receive a single subcutaneous injection of BCD-131 at a dose of 2.75 µg/kg body weight.
7. Cohort 07 will include no more than 6 volunteers who will receive a single subcutaneous injection of BCD-131 at a dose of 4.45 µg/kg body weight.

Volunteers will be included in the study in a consecutive order. First, three volunteers will be included in Cohort 01 to receive a single subcutaneous injection of BCD-131 at a calculated starting safe dose of 0.05 µg/kg. If during 14 days after the injection these volunteers do not develop any treatment-emergent Grade 3–4 adverse events, the next three volunteers will be included in the study (Cohort 02). The further inclusion algorithm is as follows:

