Subjects will be asked to stay at the study site for the first 24 h after the injection because multiple blood samples are to be collected over this period.

Regardless of the group/cohort to which a volunteer has been assigned, s/he will be followed-up for 50 days during which 16 visits will be performed.

Stage II

Stage II of the study aims to further evaluate pharmacokinetics, pharmacodynamics and safety of subcutaneous and intravenous injections of BCD-131 at a dose which ensures PD effects similar to those of the closest analogues (Mircera[®], Aranesp[®]) given as subcutaneous injections at therapeutic doses. For this purpose, 12 volunteers will be included in the study after they have signed an informed consent form, completed an examination at screening (no more than 14 days) and received the approval of the investigator confirming their eligibility for the study.

After having been randomized in a 1:1 ratio, the volunteers will be assigned to 2 groups.

- Six volunteers in Group 1 will receive a single intravenous injection of BCD-131 at a dose established at stage I of the study (Day 1).
- Six volunteers in Group 2 will receive a single subcutaneous injection of BCD-131 at a dose established at stage I of the study (Day 1).

Subjects will be asked to stay at the study site for the first 24 h after the injection because multiple blood samples are to be collected over this period. Regardless of the group/cohort to which a volunteer has been assigned, s/he will be followed-up for 50 days during which 16 visits will be performed.

3.2 Time Points for Blood Sampling to Evaluate PK at Stage I of the Study

In the groups of volunteers receiving BCD-131 and Mircera[®], blood sampling for the PK evaluation will be performed as follows:

1. PK1-1 — 5 min before the injection of BCD-131/Mircera[®]
2. PK2-1 — 30 ± 5 min after the injection of BCD-131/Mircera[®]
3. PK3-1 — $2 \text{ h} \pm 10 \text{ min}$ after the injection of BCD-131/Mircera[®]
4. PK4-1 — $8 \text{ h} \pm 15 \text{ min}$ after the injection of BCD-131/Mircera[®]
5. PK5-1 — $24 \text{ h} \pm 20 \text{ min}$ after the injection of BCD-131/Mircera[®]
6. PK6-1 — $48 \text{ h} \pm 30 \text{ min}$ after the injection of BCD-131/Mircera[®]
7. PK7-1 — $72 \text{ h} \pm 30 \text{ min}$ after the injection of BCD-131/Mircera[®]
8. PK8-1 — $96 \text{ h} \pm 60 \text{ min}$ after the injection of BCD-131/Mircera[®]
9. PK9-1 — $120 \text{ h} \pm 60 \text{ min}$ after the injection of BCD-131/Mircera[®]

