4. EVALUATION CRITERIA

4.1 Endpoints to Evaluate Single-Dose Pharmacokinetics

Primary endpoint

- $AUC_{0-1176\text{ h}}$ (area under the concentration vs. time curve from the moment of injection to 1176 h [Day 50 of follow-up]) and $AUC_{0-\infty}$ (to infinity).

Secondary endpoints

- C_{\max} (maximum serum concentration),
- T_{\max} (time to C_{\max}),
- $T^{1/2}$ (half-life),

- k_{el} (elimination constant),
- CL (total clearance).

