8.3. Accounting for missing, unavailable or doubtful data, outliers

All information specified in the e-CRFs should be supported by relevant data in source documents.

After entering all data into the electronic database, a database specialist checks it for inconsistencies, errors, and missing data points. The Clinical Study Database Manager or Medical Expert of JSC BIOCADC generates queries to correct error data or to request missing data; the queries are site-specific and subject-specific (i.e., individual queries are generated for each subject). The Clinical Study Monitor will send queries to the study site by fax or email. The queries should be resolved by the investigator within five business days from the date they have been submitted to the study site. Copies of responses to queries must be kept at the study site; original responses must be stored at JSC BIOCADC.

When responses to queries are received from investigators, the database specialist checks it for inconsistencies, errors, and missing data points. When all data at all study sites have been collected and entered, the database is closed. Afterwards, statistical processing can be started.

Missing, unused, and spurious data will not be substituted.

Spurious and unevaluable data are revealed during the outlier analysis by examination of Mahalanobis or Cook distance, visual analysis of scatter plots and box plots.

All actions taken to handle missing, unevaluable, spurious data and outliers before/during the statistical analysis will be described in the Clinical Study Report.

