8.4. The data conversion

Pharmacokinetic parameters

Based on determined concentrations in blood a number of the pharmacokinetic parameters will be calculated for the study drug:

1. **AUC₍₀₋₁₁₇₆₎**— area under the plasma concentration curve from administration to 1176 h:

- At stage I for BCD-131 and Mircera® products:

$$AUC_{(0-1176)} = \sum_{p=2}^{18} \frac{(C_p + C_{p-1}) * (t_p - t_{p-1})}{2},$$

where C_p – plasma concentration at the moment t_p (hours); $t_p \in \{0; 0.5; 2; 8; 24; 48; 72; 96; 120; 168; 216; 288; 336; 504; 672; 840; 1008; 1176\}; p=1, \dots, 18$

- At stage I for Aranesp® product:

$$AUC_{(0-1176)} = \sum_{p=2}^{20} \frac{(C_p + C_{p-1}) * (t_p - t_{p-1})}{2},$$

where C_p – plasma concentration at the moment t_p (hours); $t_p \in \{0; 0.5; 2; 8; 16; 24; 36; 48; 72; 96; 120; 168; 216; 288; 336; 504; 672; 840; 1008; 1176\}; p=1, \dots, 20$

- At stage II:

$$AUC_{(0-1176)} = \sum_{p=2}^{21} \frac{(C_p + C_{p-1}) * (t_p - t_{p-1})}{2},$$

where C_p – plasma concentration at the moment t_p (hours); $t_p \in \{0; 0.25; 0.5; 1; 2; 4; 8; 24; 48\}$

72; 96; 120; 168; 216; 288; 336; 504; 672; 840; 1008; 1176}; $p=1, \dots, 21$

2. C_{max} - maximum plasma concentration.
3. T_{max} - time until C_{max} is reached.
4. **Terminal rate constant (k_{el} , elimination constant)** will be calculated for the plasma concentration curve during the terminal log-linear phase by regression.
5. **AUC_(0-∞)** - area under the plasma concentration curve from administration to infinity:

$$AUC_{(0-\infty)} = AUC_{(0-1176)} + \frac{C_{1176}}{k_{el}},$$

where C_{1176} - plasma concentration at the moment 1176 h; k_{el} - elimination constant.

6. **Plasma concentration half-life ($T_{1/2}$)** will be calculated as:
 $T_{1/2} = \frac{\ln(2)}{k_{el}}$, where k_{el} - elimination constant.
7. **Total clearance (CL)** will be calculated as:

$$CL = \frac{D}{AUC_{(0-1176)}}, \quad \text{where } D \text{ - single dose of the drug product.}$$

Pharmacodynamic parameters

Based on reticulocyte counts and on hemoglobin values a number of key pharmacodynamic parameters will be calculated:

1. **AUEC₍₀₋₁₁₇₆₎** - (area under effect curve from the moment of injection to 1176 h [Day 50 of follow-up]) based on the change in the absolute reticulocyte count after a single-dose injection of the drug product::

$$AUEC_{(0-1176)} = \sum_{p=2}^{15} \frac{(C_p + C_{p-1}) * (t_p - t_{p-1})}{2},$$

where C_p the absolute reticulocyte count at the moment t_p (hours);

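### SAP 8.4 computes total clearance as dose over AUC(0-1176) for SC and IV groups alike, and gives AUC(0-∞) no rule for an unquantifiable 1176 h sample

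*SAP*

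**What the plan says.** SAP 8.4 gives one set of pharmacokinetic formulas for all groups.

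- Item 4: kel is estimated "during the terminal log-linear phase by regression".
- Item 5: AUC(0-∞) = AUC(0-1176) + C1176/kel, "where C_{1176} - plasma concentration at the moment 1176 h; k_{el} - elimination constant". The last quantifiable concentration is not mentioned.
- Item 7: "Total clearance (CL) will be calculated as" D/AUC(0-1176), D being the single dose. The formula makes no distinction by route and has no bioavailability term.

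SAP 4.1 lists AUC(0-1176) and AUC(0-∞) as primary and CL as secondary. SAP 3.1 gives the routes. Stage I is SC throughout (for example, "Cohort 01 will include no more than 6 volunteers who will receive a single subcutaneous injection of BCD-131"), including both reference drugs. In stage II, "Six volunteers in Group 1 will receive a single intravenous injection of BCD-131", while Group 2 is dosed SC. SAP 2.2 asks for CL after both routes in stage II, and objective 4 of that stage is: "Establish subcutaneous and intravenous doses of BCD-131 to be used in a phase II clinical study".

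On missing values SAP 8.3 says "Missing, unused, and spurious data will not be substituted". Neither document, as supplied, says how a concentration below the LLOQ is handled.

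**The concern.** Two definitions need attention, and they differ in kind.

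The clearance formula is wrong as written. Its denominator is a truncated area although the full area is computed two items earlier. More importantly, after SC dosing only the fraction F of the dose reaches the circulation, so dose over area estimates CL/F. At most 54 stage I volunteers and 6 stage II volunteers are dosed SC and only 6 are dosed IV. For up to 60 of 66 volunteers the reported total clearance would therefore be a different quantity from the one named. A reader of the stage II tables could take a pure bioavailability effect for a difference in clearance between routes, in the stage meant to inform both SC and IV doses for phase II.

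The AUC(0-∞) formula is right in one situation and silent in another. It depends on a single sample on Day 50. Doses run from 0.05 to 4.45 µg/kg (4.45/0.05 = 89-fold), so the low-dose cohorts are where that sample is most likely to be unquantifiable. A primary endpoint would then be truncated or have no value.

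**Working it through.** The documents give no half-life, F, LLOQ or numerical AUC, so there is no stated figure to reproduce. The inputs taken from them are the item 5 and item 7 formulas, the 18-point stage I grid for BCD-131 and Mircera (0 to 1176 h), the routes and the doses. Half-life, F, LLOQ and absorption rate below are assumptions.

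**1. Clearance, route.** After SC dosing AUC(0-∞) = F·D/CL, so D/AUC(0-∞) = CL/F. The ratio to true clearance is 1/F:
- F = 0.9: 1/0.9 = 1.11
- F = 0.6: 1/0.6 = 1.67
- F = 0.3: 1/0.3 = 3.33

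This factor remains whichever area is used. With the same true clearance in both stage II arms and F = 0.6, the SC arm would show a value 67% higher than the IV arm.

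**2. Clearance, truncation.** For a one-compartment IV curve the share of area beyond 1176 h is f = 2^(−1176/t½), and D/AUC(0-1176) exceeds D/AUC(0-∞) by the factor 1/(1 − f):
- t½ 140 h: f = 2^(−8.40) = 0.0030, excess 0.3%
- t½ 200 h: f = 2^(−5.88) = 0.0170, excess 1.7%
- t½ 250 h: f = 2^(−4.70) = 0.0384, excess 4.0%

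**3. AUC(0-∞), 1176 h sample quantifiable.** Then tlast = 1176 h and Clast = C1176, so item 5 is the standard formula and the ratio is exactly 1.

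**4. AUC(0-∞), 1176 h sample not quantifiable.** If C1176 is set to 0, the added term is 0/kel = 0 and AUC(0-∞) = AUC(0-1176). If it is treated as missing and not substituted, item 5 has no value.

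To size the first case I used a one-compartment SC curve, C(t) = ka/(ka − k)·(e^(−kt) − e^(−ka·t)), with F·D/V set to 1. The exact area is 1/k. Values below LLOQ were set to 0.

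Worked example, absorption half-life 24 h, elimination half-life 200 h, LLOQ 30% of Cmax:
- k = ln2/200 = 0.003466; ka = ln2/24 = 0.02888; exact area = 1/k = 288.5.
- Cmax = 0.749, so LLOQ = 0.225. C(336 h) = 0.355 is quantifiable; C(504 h) = 0.198 is not.
- SAP formula: the trapezoid sum is 212.8 and the tail is 0. Recovery is 212.8/288.5 = 74%.
- Last-quantifiable formula: AUC(0-336) = 183.0, and Clast/k = 0.3546/0.003466 = 102.3. Recovery is 285.3/288.5 = 99%.
- Item 7 on the same curve: 288.5/212.8 = 1.36, so D/AUC(0-1176) is 36% above CL/F.

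Recovery of the exact area by item 5, absorption half-lives 12 and 24 h, elimination half-lives about 25–250 h:

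| LLOQ as share of Cmax | Item 5, values below LLOQ = 0 |
|---|---|
| 30% | about 74–90% |
| 10% | about 92–98% |
| 3% or less | about 98–101% |

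These ranges come from a coarse set of half-lives, and their ends depend on how the half-life falls against the sampling times. At 25.5, 50, 100, 140, 200 and 250 h the middle row is 92–97%. Stepping the half-life by 0.5 h widens the rows to 68–90%, 89–99% and 97–101%. The pattern does not change. At the same six half-lives and LLOQ 30%, the last-quantifiable formula recovers 95–100%, but with the true k inserted.

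**The case against.** The strongest reply is that item 5 is the usual formula whenever the Day 50 sample can be measured, and that the two truncation faults tend to cancel. If C1176 is truly negligible, D/AUC(0-1176) is nearly right for IV data; if it is sizeable, it will be quantifiable and AUC(0-∞) is right. The first part stands. The second holds only when the assay is sensitive relative to Cmax: in the worked example C1176 is unquantifiable, yet about a quarter of the area is lost.

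The size of the AUC effect rests on an LLOQ that the documents do not give. At 3% of Cmax or less it is trivial. The benefit of extrapolating from Clast is also somewhat flattered above, because at a high LLOQ few post-peak points remain and the fitted kel would be uncertain. The protocol supplied is its synopsis, so a bioanalytical rule elsewhere cannot be excluded. It would settle the AUC point but not the clearance definition. SAP 8.2 allows the list of statistical methods to grow, but that concerns the choice of tests and does not correct a stated parameter formula.

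Three stronger readings are tempting and not supported:
- *One missed sample removes two trapezoids from the AUC.* Nothing in the SAP says so. Joining the neighbouring samples is not substitution, and SAP 8.3 requires the handling of missing data to be described in the study report.
- *Truncation will produce a false finding of non-proportional kinetics.* No dose-proportionality analysis is named, so this is conjecture about later interpretation.
- *The plan fails because it does not estimate F.* F is not a listed objective or endpoint. Dose selection for stage II is described in terms of pharmacodynamic similarity, with pharmacokinetics and safety. Both stage II arms receive the stage I dose, so F can be read from the AUCs already reported.

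**Conclusion.** The concern holds for clearance without qualification and for AUC(0-∞) conditionally.

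Clearance in item 7 is misdefined for every group and mislabelled for all SC groups. The label error dominates, at 1.1 to 3.3 times over the assumed range of F. Truncation alone is at most about 4% up to a 250 h half-life if every sample is quantifiable. CL is a secondary endpoint, which limits the consequence.

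A reader might infer that the primary AUC(0-∞) is wrong in general. It is not. The gap is the missing rule for subjects whose last quantifiable sample comes before 1176 h. Its size runs from nothing to roughly a quarter of the area or slightly more, depending on assumed LLOQ and half-life, and it is most likely in the low-dose cohorts. This should be corrected, but it does not invalidate the design.

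**What to change.** Amend SAP 8.4:

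- Item 5: AUC(0-∞) = AUC(0-tlast) + Clast/kel, with tlast the last quantifiable sample. State how values below LLOQ are treated, the minimum number of points for kel, and the extrapolated share above which the value is flagged.
- Item 7: CL = D/AUC(0-∞) for the stage II IV group only. Report D/AUC(0-∞) as CL/F for all stage I groups and stage II Group 2, in separate table rows, and carry the label into SAP 4.1.
- Optional: report the dose-normalised stage II SC/IV ratio of AUC(0-∞) as a descriptive estimate of F, recognising that it rests on six volunteers per arm in parallel groups.

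The cost is a few lines of SAP text and standard non-compartmental settings. No extra samples, volunteers or visits are needed.

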8.5. Multivariate Comparison and Multiplicity

Refer to Section 8.2.

8.6. Subgroup analysis, interaction and related variables

Not available.

9. OTHER PLANNED ANALYSES

No additional analyses are planned in this study.

10. DEVIATIONS FROM ANALYSIS METHODS DESCRIBED IN STUDY PROTOCOL

This Statistical Analysis Plan has no deviations from methods described in Study Protocol.
